5.6.5 Listeremia

Persistent (for 48-72 hours) symptoms consistent with listeremia (e.g., fever and muscle aches, often preceded by diarrhea or other gastrointestinal symptoms) will require obtaining a quantitative blood culture. Symptoms that persist for >72 hours following dosing must be treated with an IV course of an appropriate antibiotic such as amoxicillin, ampicillin, ciprofloxacin, erythromycin, gentamycin, penicillin, trimethoprim/sulfamethoxazole, or vancomycin. ADXS11-001 is resistant to both streptomycin and chloramphenicol. Clinical sepsis requiring intensive care admission and/or pressors will automatically result in discontinuation of further doses.

5.7 Diet/Activity/Other Considerations

5.7.1 Diet

Subjects should maintain a normal diet unless modifications are required to manage an AE such as diarrhea, nausea or vomiting.

5.7.2 Contraception

The study drug(s) may have adverse effects on a fetus in utero. Furthermore, it is not known if the study drug(s) has transient adverse effects on the composition of sperm. Non-pregnant, non-breast-feeding women may be enrolled if they are willing to use 2 methods of birth control or are considered highly unlikely to conceive. Highly unlikely to conceive is defined as 1) surgically sterilized, 2) postmenopausal (has not had menses for greater than 1 year), or 3) not heterosexually active for the duration of the study. The 2 birth control methods can be either 2 barrier methods or a barrier method plus a hormonal method to prevent pregnancy. Males may enroll if they are willing to use 1 method of birth control. Subjects should start using birth control from screening throughout the study period up to 120 days after the last dose of study therapy.

The following are considered adequate barrier methods of contraception: diaphragm, condom (by the partner), copper intrauterine device, sponge, or spermicide. Appropriate hormonal contraceptives will include any registered and marketed contraceptive agent that contains an

estrogen and/or a progestational agent (including oral, subcutaneous, intrauterine, or intramuscular agents).

Subjects should be informed that taking the study medication may involve unknown risks to the fetus (unborn baby) if pregnancy were to occur during the study. In order to participate in the study they must adhere to the contraception requirement (described above) for the duration of the study and during the follow-up period defined in Section [7.2.2](#) - Reporting of Pregnancy and Lactation to the Sponsor. If there is any question that a subject will not reliably comply with the requirements for contraception, that subject should not be entered into the study.

5.7.3 Use in Pregnancy

If a subject inadvertently becomes pregnant while on treatment, the subject will immediately be removed from the study. The site will contact the subject at least monthly and document the subject's status until the pregnancy has been completed or terminated. The outcome of the pregnancy will be reported to the sponsor without delay and within 24 hours if the outcome is a serious adverse experience (e.g., death, abortion, congenital anomaly, or other disabling or life-threatening complication to the mother or newborn). The study investigator will make every effort to obtain permission to follow the outcome of the pregnancy and report the condition of the fetus or newborn to the sponsor. If a male subject impregnates his female partner the study personnel at the site must be informed immediately and the pregnancy reported to the sponsor and followed as described above and in Section [7.2.2](#).

5.7.4 Use in Nursing Women

It is unknown whether the study drug(s) is excreted in human milk. Since many drugs are excreted in human milk, and because of the potential for serious adverse reactions in the nursing infant, subjects who are breast-feeding are not eligible for enrollment.

5.8 Subject Withdrawal/Discontinuation Criteria

Subjects may withdraw consent at any time for any reason or be dropped from the trial at the discretion of the investigator should any untoward effect occur. In addition, a subject may be withdrawn by the investigator or the Sponsor if enrollment into the trial is inappropriate, the trial plan is violated, or for administrative and/or other safety reasons. Specific details regarding discontinuation or withdrawal are provided in Section [7.1.3](#) – Other Procedures.

A subject must be discontinued from the trial, with no further data reporting, for the following reasons:

- The subject withdraws consent
- Subject death
- The subject is lost to follow-up

A subject must be discontinued from study treatment, but will continue to be followed, for the following reasons:

- Confirmed radiographic disease progression
 - *Note:* For unconfirmed radiographic disease progression, please see RECIST 1.1 criteria
 - *Note:* A subject may continue on treatment with confirmed radiographic progression if clinically stable or clinically improved, please see RECIST 1.1 criteria, after discussion with the sponsor.
- Unacceptable adverse experiences as described in Section [7.2](#)
- Investigator's decision to withdraw the subject
- The subject has a confirmed positive serum pregnancy test
- Noncompliance with trial treatment or procedure requirements
- Completed 12 months of treatment with study drug(s)
 - *Note: 12 months of study medication is calculated from the date of first dose. Subjects who stop treatment after 12 months may be eligible for additional study treatment if they progress after stopping study treatment provided they meet the requirements detailed in Section [7.1.4.2.1](#).*
- Administrative reasons
- Sponsor decision to terminate the trial

- Subject is determined to have met one or more of the exclusion criteria for study participation at study entry and continuing investigational therapy might constitute a safety risk

The End of Treatment and Follow-up visit procedures are listed in Section [6.0](#) - Study Flow Chart and Section [7.1.4](#) -Visit Requirements. After the end of treatment, each subject will be followed for 30 days for adverse event monitoring (90 days for serious adverse event monitoring or the initiation of a new anticancer therapy as described in Section [7.2.3.1](#)). Subjects who discontinue for reasons other than progressive disease will have post-treatment follow-up tumor assessments until disease progression, initiating a non-study cancer treatment, withdrawing consent or becoming lost to follow-up.

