2.2 ADXS11-001 vs MEDI4736 vs ADXS11-001 +MEDI4736

Part B of the study will start once subjects from Part A have been followed through the 28-day DLT period. Part B will be a Phase 2 design which will randomize subjects 1:1:2 to ADXS11-001 : MEDI4736 : ADXS11-001+MEDI4736. Randomization will be stratified based upon disease type. ADX11-001 will be administered every 4 weeks. MEDI4736 will be administered every 2 weeks. [REDACTED]

[REDACTED] Subjects will continue on therapy for up to 1 year or until they discontinue due to documented progression, unacceptable toxicity, investigator's decision to withdraw the subject, subject withdraws consent, pregnancy of the subject, noncompliance with trial treatments or procedure requirements, administrative reasons, or withdrawal from the study. Subjects who achieve a complete response (CR) should receive at least 1 additional cycle of treatment. Crossover to another treatment arm will not be allowed. Adverse events will be monitored throughout the study and graded in severity according to the guidelines outlined in the National Cancer Institute (NCI) Common Terminology Criteria for Adverse Events (CTCAE) version 4.03.

After the end of treatment, each subject, regardless of whether they participate in Part A or Part B, will be followed for a minimum of 30 days for adverse event monitoring (serious adverse events will be collected for up to 90 days) after the end of treatment. Subjects will have post treatment follow up visits for disease status, including non-study cancer treatment and disease progression, for up to 3 years.

Safety and efficacy analysis will be performed for both parts of the study. Subject disposition, demographic and baseline characteristics will be summarized separately for Part A and Part B. Adverse events will be classified and summarized by system organ class (SOC) and preferred term, incidence, severity, and causality. All subjects who receive at least 1 dose of study drug will be included in the safety analyses.

[figure not shown]
Statistical analysis for efficacy will be performed by treatment arm and disease type. Although it may lack statistical power, statistical testing for treatment comparisons will be

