7.1.2.9 Immune-Related Response in Measureable Lesions (irRECIST)

In addition to evaluation using RECIST 1.1 criteria, an immune response adaptation of RECIST will be applied to this trial. The essential differences between irRECIST and RECIST criteria are as follows:

New measureable lesions do not necessarily constitute progressive disease and they should be added into the total tumor burden. New non-measurable lesions do not constitute disease progression but will prevent the determination of an irCR.

Apparent disease progression should be confirmed after 4 weeks in the absence of symptoms consistent with clinical deterioration.

At baseline, the sum of the longest diameters (SumD) of all target lesions (2 per organ and 5 in total) is measured. At each subsequent tumor assessment, the SumD of the target lesions and of new, measurable lesions (≥ 10 mm [lymph nodes ≥ 15 mm in shortest diameter]; up to 2 new lesions per organ, total 5 new lesions) are added together to provide the total measurable tumor burden (TMTB):

$$\text{TMTB} = \text{SumD target lesions} + \text{SumD new, measurable lesions}$$

Percentage changes in TMTB per assessment time point describe the size and growth kinetics of both old and new measurable lesions as they appear. At each tumor assessment, the response in target and new measurable lesions is defined based on the change in TMTB (after ruling out irPD) as follows:

- Complete Response (irCR): complete disappearance of all target and new, measurable lesions, with the exceptions of lymph nodes which must decrease to <10 mm in short axis
- Partial Response (irPR): decrease in TMTB $\geq 30\%$ relative to baseline (see below)
- Stable Disease (irSD): not meeting criteria for irCR or irPR, in absence of irPD
- Progressive Disease (irPD): increase in TMTB $\geq 20\%$ relative to nadir

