7.1.2.12 Overall Response

Overall response will be determined based on RECIST 1.1 criteria and by irRECIST criteria (Table 1). Overall response according to irRECIST is derived from the responses in measurable lesions (based on TMTB) and the presence of any non-measurable lesions.

Table 6 Tumor Response Evaluation: Comparison of RECIST 1.1 and irRECIST

Criteria	RECIST1.1	irRECIST
New measurable lesions (≥ 10 mm)	Always represents PD	Incorporated into tumor burden
New non-measurable lesions (< 10 mm)	Always represents PD	Does not define progression but precludes irCR
Non-Target lesions	Changes contribute to defining BOR of CR, PR, SD, and PD	Contribute to defining irCR (complete disappearance required)
CR	Disappearance of all lesions	Disappearance of all lesions
PR	$\geq 30\%$ decrease in the sum of the longest diameter of all target lesions compared with baseline, in absence of new lesions or unequivocal progression of non-target lesions	$\geq 30\%$ decrease in tumor burden compared with baseline
SD	Neither sufficient shrinkage to qualify for PR nor sufficient increase to qualify for PD, taking as reference the smallest sum diameters while on study	Neither a 30% decrease in tumor burden compared with baseline nor a 20% increase compared with nadir can be established
PD	At least 20% increase in sum of diameters of target lesions, taking as reference the smallest sum on study. In addition to the relative increase of 20%, the sum must also demonstrate an absolute increase of at least 5mm. The appearance of one or more new lesions is also considered progression.	At least 20% increase in tumor burden compared with nadir (at any single time point) ^a

irRECIST = immune-related Response Evaluation Criteria in Solid Tumors; BOR = best overall response; CR = complete response; irCR = immune-related complete response; PD = progressive disease; PR = partial response; SD = stable disease;

^a Patients with an initial finding of progressive disease (irPD) before or at the 9-week imaging assessment, but without rapid clinical deterioration, require confirmation of irPD with a second, consecutive scan obtained ≥ 4 weeks from the initiation documentation. Patients will continue to receive study treatment until irPD is confirmed at this later time point. Best overall response (BOR) will therefore include responses occurring at any time before disease progression and after early progression (i.e., within the first 8 weeks of the study).

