8.0 STATISTICAL ANALYSIS PLAN

8.1 Statistical Analysis Plan Summary

This is a Phase 1-2 study of ADXS11-001 or MEDI4736 alone or combination in locally advanced, or metastatic, squamous or non-squamous carcinoma of the cervix or HPV+ squamous cell carcinoma of the head and neck.

There are 2 phases in this study with different objectives. For safety, the analysis will be performed for Part A and Part B separately and combined. The efficacy analysis will be performed for Part A and Part B separately. SAS 9.2 or higher will be used for data analysis.

Subject disposition, demographic and baseline subject characteristics will be summarized separately for Part A and Part B. Adverse events will be classified and summarized by type, incidence, severity, and causality. All adverse events will be summarized by subject, treatment, and disease. All subjects who receive at least 1 dose of study treatment will be included in the safety analyses.

Statistical analysis for efficacy will be summarized by treatment arm and disease type. Although it may lack statistical power, statistical testing for treatment comparisons will be performed as a reference. Tumor response will be evaluated by RECIST criteria and secondarily by irRECIST criteria. The overall response rate will be summarized; frequency counts and percentage and will be tested by the Fisher's Exact test. PFS is defined as the time from randomization until objective tumor progression or death. Subjects who have not progressed or who are still alive at the time of evaluation will be censored for the analysis. Kaplan-Meier (KM) curves and descriptive statistics will be used to summarize PFS. The percentage of subjects with PFS and the 95% confidence intervals will be provided. PFS and duration of response will be summarized using KM method and tested by the Log-Rank test controlled by disease type.

Furthermore, the disease response will be tabulated for all subjects who receive ADXS11-001 monotherapy, MEDI4736 monotherapy or ADXS11-001 + MEDI4736 combination therapy.

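### A subject taken off treatment on RECIST 1.1 progression that is not irPD has no later scheduled scan and is then censored in irRECIST PFS, which biases that PFS upward by an amount the documents do not fix

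*Combined protocol and SAP*

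**What the plan says.** **Scans after treatment.** Section 5.8: "Subjects who discontinue for reasons other than progressive disease will have post-treatment follow-up tumor assessments until disease progression". Section 7.1.4.3.2 and the imaging footnotes to flow charts 6.1 to 6.4 carry the same restriction.

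**When treatment stops.** Section 2.2 has subjects on therapy "until they discontinue due to documented progression", and section 2.1 agrees. Section 5.8 instead lists "Confirmed radiographic disease progression" and adds: "For unconfirmed radiographic disease progression, please see RECIST 1.1 criteria". It gives no irRECIST counterpart.

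**What irRECIST counts as progression.** Section 7.1.2.9: "New measureable lesions do not necessarily constitute progressive disease and they should be added into the total tumor burden", and "Apparent disease progression should be confirmed after 4 weeks in the absence of symptoms consistent with clinical deterioration". Table 6 makes any new lesion PD under RECIST 1.1. Under irRECIST it adds a new measurable lesion to the tumour burden and lets a new non-measurable lesion rule out irCR only. Section 7.1.2.11 agrees. Table 8 does not: there an unequivocal new lesion gives irPD whatever else is seen.

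**How PFS is analysed.** Section 3.4 names PFS by both criteria under the Part B primary objective. Section 8.1 gives one event definition (objective progression or death) and one censoring rule: "Subjects who have not progressed or who are still alive at the time of evaluation will be censored for the analysis".

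**The concern.** The trial uses two definitions of progression but has one censoring rule and one point at which imaging stops. Where RECIST 1.1 calls progression and irRECIST does not, the subject can leave the imaging schedule with no irRECIST event on record. The subject is then censored because the disease got worse, so censoring is not independent of prognosis. Kaplan-Meier treats that subject as having the same outlook as those still at risk, and the curve is too high. The estimate affected belongs to the Part B primary objective, in arms of about 12, 12 and 24 subjects (48 allocated 1:1:2), where a few subjects can move a curve.

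**Working it through.** The plan states no assumed median PFS, event count or frequency of discordant progression, so there is no figure to reproduce. The check traces the rules and then adds an illustration.

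**Tracing one subject**

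1. A scan shows a new lesion while target and known non-target disease is stable. RECIST 1.1: PD (section 7.1.2.8, Table 6).
2. irRECIST: if the lesion is non-measurable, this is not irPD (section 7.1.2.11, Table 6). If it is measurable, its diameter is added to the burden, and irPD needs a rise of at least 20% from nadir. With targets at their nadir sum S, one new 10 mm lesion reaches that only if 10/S ≥ 0.20, that is S ≤ 50 mm. For a larger S the subject is not irPD.
3. Treatment is stopped for documented progression (sections 2.1, 2.2). The reason is progression, so section 5.8 schedules no further imaging.
4. irRECIST PFS: no irPD and no death, so the subject is censored under section 8.1. The censoring date is not stated. At the last tumour assessment, the usual convention, it falls at about the time of RECIST progression. At last contact, it falls later and adds event-free time.
5. If a later death is captured, it becomes the event, at a time later than the progression. The direction is still upward.

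Step 4 reads the censoring sentence as meaning neither progressed nor dead, as section 2.2 words it. The literal wording in 8.1 could censor any living progressor; that is a separate drafting point.

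**Illustration (every input is an assumption)**

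PFS is exponential with true median m; 10% of events are deaths and 90% progressions; a fraction q of progressions is censored at the progression date, with no later death captured.

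- Counted hazard = [0.10 + 0.90(1 − q)] × true hazard = (1 − 0.9q) × true hazard
- Apparent median = m/(1 − 0.9q)

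For m = 4.0 months:

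- q = 0.10: 4.0/0.91 = 4.4
- q = 0.25: 4.0/0.775 = 5.2
- q = 0.50: 4.0/0.55 = 7.3

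A simulation of 200,000 subjects, with progression seen only on an 8-week scan grid, gave these Kaplan-Meier 6-month PFS values:

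| True median (months) | q = 0 | q = 0.10 | q = 0.25 | q = 0.50 |
|---|---|---|---|---|
| 2 | 0.14 | 0.18 | 0.25 | 0.40 |
| 4 | 0.38 | 0.42 | 0.49 | 0.61 |
| 6 | 0.53 | 0.56 | 0.62 | 0.71 |

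On that grid the Kaplan-Meier median moves in 8-week steps. For m = 4 it is 5.52 months at q = 0, 0.10 and 0.25, and 9.21 at q = 0.50. The 6-month rate therefore shows the bias more reliably than the observed median.

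**The case against.** The strongest reply is that the plan already keeps subjects on treatment until progression is confirmed. Section 5.8 makes confirmed progression the reason to stop, and the Table 6 footnote says that early irPD without rapid deterioration will "require confirmation of irPD with a second, consecutive scan", with treatment continuing meanwhile. On that path the confirming scan comes before imaging stops and q is 0. This stands for those subjects. It does not cover the case traced above: the footnote concerns irPD before or at the 9-week scan, not RECIST PD that is not irPD. Section 5.8 does not say by which criteria progression is confirmed, and sections 2.1 and 2.2 do not mention confirmation.

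Second, Table 8 would make an unequivocal new lesion irPD and so an event. That is correct if Table 8 governs, but it contradicts section 7.1.2.9, section 7.1.2.11 and Table 6. The same subject is an event or censored depending on the passage used.

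Third, follow-up does not end altogether. Section 2.2 provides disease-status visits for up to 3 years, the flow charts mark imaging at the discontinuation visit, and death remains an event. But the disease-status visits are not said to include scans, and the discontinuation scan is taken at stopping, so it adds no later follow-up.

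Fourth, section 8.1 calls the treatment comparisons a reference that may lack power, and puts irRECIST second for tumour response. This limits the consequences. It does not make the estimate unbiased.

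**Conclusion.** The point holds in a limited form. For subjects taken off treatment on RECIST 1.1 PD that is not irPD under section 7.1.2.9, section 7.1.2.11 and Table 6, the scan-stop and censoring rules together produce informative censoring, and irRECIST PFS is biased upward. The size is unknown because the documents do not fix q. The change from 4.0 to about 5.2 months at q = 0.25 is an illustration under the stated assumptions, not an estimate for this trial.

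Three stronger readings are tempting and are not supported:

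- *Everyone stopped for progression is censored in irRECIST PFS.* Subjects kept on treatment until irPD is confirmed are not, nor are new-lesion subjects if Table 8 applies.
- *Unconfirmed irPD is censored as the plan is written.* No passage makes confirmation a condition for a PFS event, and Table 6 defines irPD on a single assessment. The status of unconfirmed irPD is simply not stated.
- *The rule creates a spurious hazard ratio between arms.* Part B is open-label, so stopping habits could differ by arm, but the documents give no basis for saying that they will or by how much.

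**What to change.** In section 8.1, add a rule for irRECIST PFS along these lines:

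> *Progression that led to discontinuation of treatment (RECIST 1.1 PD or unconfirmed irPD) and is followed by no later tumour assessment is an event on the date of that progression. A sensitivity analysis censors these subjects at their last assessment.*

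State there also whether an irRECIST PFS event otherwise needs confirmation and which date then counts. Report the number of subjects affected in each arm.

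Reconcile two sets of passages: Table 8 with section 7.1.2.9, section 7.1.2.11 and Table 6 on new lesions; and documented progression in sections 2.1 and 2.2 with confirmed progression in section 5.8. Which stopping rule applies is for the sponsor and investigators to settle; the analysis needs only one consistent statement.

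The cost is SAP wording, one sensitivity analysis and consistency edits, with no extra scans or visits. The downside is that irRECIST PFS moves closer to RECIST 1.1 PFS, because some RECIST-only progressions now count in both. The sensitivity analysis shows how much that matters.
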